2.4 Sample Size and Power Calculations

For all Aims there is sufficient sample size to detect clinically meaningful differences with 90% power, described below:

2.4.1. Specific Aim 1. We use the Finnegan NAS score as the primary outcome for this aim. From Nayeri et al. [70] and our own pilot data, the Finnegan NAS score in opioid-exposed infants had a SD of 2.0-2.5. Assuming a standard t-test with a two-sided alpha level of 0.05 for the unadjusted comparison of the Finnegan scores at a particular time point with the more conservative standard deviation (SD.=2.5), the sample size of 115/group can detect a difference of 1.1 with 90% power. Taking into account the repeated measures of the Finnegan NAS score, assuming intra-infant correlations of 0.5-0.7, we will have 90% power to detect a difference of 0.80-0.95 in a mixed effects model for the overall (i.e., across time) treatment group coefficient. With a mixed effects model, we will also add covariates as described above to determine an adjusted treatment effect. We expect that this model may have even more power than described here due to the partitioning of the overall variance among the covariates. Because infants are hospitalized and under observation until release, we expect only minimal attrition and loss of information.

2.4.2. Specific Aim 2. We use Movement as primary outcome for this aim. Based on our preliminary data in 26 NAS infants (OFF: mean movement 40% of condition time, SD=10%; ON: mean movement 26% of condition time, SD=9%) and

assuming a two-sided paired t-test at alpha=0.05 for the unadjusted treatment effect, we estimate 25 infants per group will give us 90% power to detect a reduction of 7% in movement between the two treatment groups (a relative reduction of about 20% from 40% in OFF to 33% in ON) with a conservative SD of 10% (from the pilot study).

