4.3.2 Specific Aim 1: We will use mixed effects models as described above to examine whether infants treated with SVS compared to SCC have: 1) Lower daily average and maximum NAS scores; 2) Less morphine requirement (primary pharmacological treatment for managing NAS at both sites; cumulative dose normalized for body weight); 3) Enhanced velocity of weight gain throughout hospitalization; and 4) Shorter hospitalization length of stay. A model will be fit for each outcome using Nagelkerke's R² to determine the model with the best fit using the ratio of the -2 log likelihoods for the model with covariates compared to the intercept-only model. Factors of interest will be included in the model as appropriate and interactions with treatment group will be tested as well. The interactions will indicate whether the treatment effect is the same across subgroups. Additional analyses to identify groups of infants who do particularly well (or poorly) with SVS will be conducted using latent class techniques, such as cluster analysis (for continuous variables) or latent class analysis (for discrete variables). The factors of interest will include: drug exposure (e.g., prescribed maintenance therapy, prescription drugs and illicit substance; with or without poly-drug use), demographic data (gender, race, gestational age, birth weight, birth head circumference, delivery mode, anesthesia at delivery), and feed type (formula or breast milk).

Movement: Actigraphy (movement activity frequency) will be compared across days and between Groups using similar mixed effects models as above. The outcomes of interest are actigraphy throughout hospitalization to determine if SVS reduces movement and increases quiescence episodes over time (12 and 24 hour assessments) compared to SCC.

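### Section 4.3.2 looks for infants who do well or poorly with SVS by clustering, but states no class inputs and no SCC comparison within class, so the classes cannot be read as responders

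*Combined protocol and SAP*

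**What the plan says.** Section 4.3.2 fits mixed effects models to each Aim 1 outcome, chooses the best-fitting model by Nagelkerke's R², and adds that "interactions with treatment group will be tested as well". The purpose is given in the next sentence: "The interactions will indicate whether the treatment effect is the same across subgroups".

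The section then turns to a separate exercise: "Additional analyses to identify groups of infants who do particularly well (or poorly) with SVS will be conducted using latent class techniques". The examples are cluster analysis for continuous variables and latent class analysis for discrete ones.

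The sentence after that begins "The factors of interest will include: drug exposure" and goes on to demographic and birth variables and feed type. It does not say whether these factors form the classes or are the covariates of the mixed models.

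The section does not state which variables form the classes, whether one or both arms enter, how many classes there will be, or how a class in SVS is compared with SCC. The interaction tests are not linked to the classes.

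**The concern.** Doing well with SVS means doing better than the same infant would have done under SCC. In a parallel-group trial each infant has one arm, so this is not observed for any infant. It can be estimated only as a difference between randomised arms within a group. Cluster and latent class methods do not estimate that difference. They find groups that are alike on whatever variables are entered.

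If the variables are outcomes, the groups will be milder and more severe NAS. If they are baseline factors that predict severity, classes compared only among SVS infants will differ for the same reason. Either result could be reported as a responder profile and could misdirect later use or study of SVS.

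The companion sentence on interactions has a related weakness. Testing can detect a difference in effect, but a non-significant test in a trial sized for the main effect says little about whether effects are the same.

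**Working it through.** **The plan's own figure (section 2.4.1).** Inputs: 115 infants per group, SD 2.5, two-sided alpha 0.05, power 90%. The detectable difference is (1.960 + 1.2816) × 2.5 × √(2/115) = 3.2415 × 0.3297 = 1.07 points (also 1.07 by the t-test), which the plan gives as 1.1. Power at exactly 1.1 is 91.6% (normal) or 91.3% (t-test). The figure reproduces.

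**Clustering SVS infants on outcomes, with no SVS effect.** The documents supply 115 per arm, SD 2.5 and intra-infant correlation 0.5-0.7. Assumed: 10 scores per infant, mean score 10, two classes by k-means on each infant's mean and maximum score; 1,500 simulated trials.

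| | correlation 0.5 | correlation 0.7 |
|---|---|---|
| Gap between the two SVS classes (NAS points) | 2.9 | 3.4 |
| Better SVS class below the SCC mean | 1.5 | 1.7 |
| That difference significant at 0.05 | 99.9% | 99.9% |

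A hand check agrees. The SD of a mean of 10 scores is √(6.25 × (0.5 + 0.5/10)) = 1.85, or √(6.25 × (0.7 + 0.3/10)) = 2.14. Splitting a normal variable at its mean gives a gap of 2√(2/π) = 1.596 SDs, which is 2.96 or 3.41 points. Half of that, 1.48 or 1.70, is the distance below the overall mean.

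A second simulation clustered on NAS score, length of stay (SD 6 days, assumed) and dose. With correlations of about 0.65-0.7 among the three, the NAS gap was 3.56 points and the better class was 1.79 below the SCC mean. The SCC arm, clustered the same way, split by 3.53, so the split has nothing to do with SVS. With correlations of 0.2-0.3 the gap was 2.7-2.9 points and the better class 1.3-1.5 below the SCC mean. The documents give no such correlations, so only the range of 2.7 to 3.6 and 1.3 to 1.8 should be used.

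**Baseline classes, with no SVS effect.** Assumed: four baseline factors, two of which explain about 34% of between-infant variance.
- Classes compared within SVS only: significant in 95% (correlation 0.5) and 96% (0.7) of trials.
- Classes formed in both arms, class-by-treatment interaction tested: significant in 4.2% and 4.9%.

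**Both arms clustered on outcomes, class membership tested against arm:** significant in 5.9% and 5.1%. The false finding comes from leaving out the randomised comparison.

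**Interactions.** For a factor splitting infants p to 1 − p, the standard error of the difference in effect is 1/√(p(1 − p)) times that of the main effect: 2 for 50/50 and 1/√(0.2 × 0.8) = 2.5 for 20/80. For a difference in effect as large as the main effect detectable with 90% power:
- 50/50: Φ(3.2415/2 − 1.96) = Φ(−0.339) = 37%.
- 20/80: Φ(3.2415/2.5 − 1.96) = Φ(−0.663) = 25%.

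The section lists nine factors: drug exposure, seven demographic or birth variables, and feed type. With one independent test each, the chance of at least one false interaction per outcome is 1 − 0.95⁹ = 37%.

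**The case against.** The section does not say that NAS scores are the class-forming variables, nor that only SVS infants are clustered. A reader might infer that the analysis sorts infants by severity, but the only variables listed nearby are exposure, demographic and feeding factors. Their mix of continuous and discrete items fits the two techniques named, so a baseline reading is at least as natural. This stands.

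A reader might also infer that a responder group must appear even if SVS does nothing. That too is more than the text supports. It happens when outcomes are clustered within SVS or when classes are compared within SVS only, and the text commits to neither. Two-class k-means always returns two classes, so the mere existence of a better class is a product of the setting. The informative results are the size of the gap and its significance against SCC.

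The plan does test treatment interactions in both arms, which is a proper route to effect modification. But these tests are not applied to the classes, so they do not repair the clustering analysis.

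On the interactions, the plan gives no rule for reading a non-significant result as equal effects. Low power for interactions is common to trials sized for a main effect, and the nine tests are unlikely to be independent or all single-degree-of-freedom. These points reduce the weight of the secondary issue. The stated purpose still goes beyond what the tests can show.

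**Conclusion.** The concern holds as a mismatch between question and method. Clustering does not identify who benefits from SVS, and the plan states no step that brings in the comparison with SCC. That conclusion needs no simulation.

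The magnitudes are illustrative. They rest on two classes, the assumed inputs and correlations, and the assumed prognostic strength of the baseline factors. Under those assumptions, the two unsafe ways of carrying out the analysis produce a false better class nearly always, with an apparent advantage over SCC of about 1.3 to 1.8 points when outcomes are clustered. The error rate is near 5% when classes are tested against randomised arm.

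The interaction sentence is secondary: power is about 37% or 25%, and the 37% false-positive figure is conditional on independence.

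A reader might infer that the trial's main result is at risk. It is not: these are described as additional analyses, and the SVS versus SCC comparison of the NAS score stands apart from them. The change should be made, but it is not critical to the trial.

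**What to change.** In section 4.3.2:

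1. Form classes only from variables known before randomisation, in both arms pooled, blind to arm and outcome. Name the variables and the rule for the number of classes in advance. Feed type is charted during the hospital stay (section 4.1.1), can be settled after randomisation, and should not define a class.
2. Estimate SVS minus SCC within each class with a 95% CI, and test class-by-treatment. Label the result exploratory.
3. Replace the sentence on the purpose of the interactions with a statement that differences in effect will be reported with 95% CIs and that non-significance will not be read as equal effects.
4. Take the main treatment coefficient from a model without interaction terms. Because the model is chosen by best fit, a retained interaction could otherwise turn that coefficient, under the usual coding, into the effect at one level of a factor.

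The cost is SAP wording and a little programming. The downside is fewer striking exploratory findings.

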2.1.1. Investigational Device. Stochastic Vibrotactile Stimulation (SVS). The

infant's crib mattress will be replaced with a specially constructed mattress (noncommercially available) to provide gentle vibrations and sounds during mattress stimulations. The mattress is embedded with mechanical actuators that provide wholebody SVS (30-60Hz; ~10-12µm RMS). Co Fab Design, LLC will construct the mattresses and drivers as per the design documents furnished under Confidentiality Disclosure Agreement (CDA; University of Massachusetts Medical School/Wyss Institute-Harvard University patent: PCT/US2015/021999) for research purposes only as per the licensed mattress assembly and electrical assembly and verification documentation; device components may be modified with improved technologies that provide equivalent mattress output to help ensure consistency of mattress integrity over time. Engineers from the Wyss Institute and the University of Pittsburgh will provide assistance in the build to ensure it performs as per the original patent documentation.

2.1.2. Study Design/Type. This study is a randomized, placebo-controlled, parallel group clinical trial. Eligible patients will be randomized into one of two groups in a 1:1 ratio, matched for gender, to either (1) SVS or (2) SCC:

1) SVS. Experimental Intervention: Newborn infants at-risk for NAS due to opioid exposure *in utero* randomized to this arm will receive daily intervals of continuous SVS (ON) and no SVS (OFF) throughout hospitalization, starting within 30-hrs post birth. An automated control box will be set to deliver continuous alternating 3-hr cycles of ON/OFF intervals. A stimulation period will always be followed by an interval of no stimulation; in any 24-hr period an infant will not receive more than a total of 12 hrs of stimulation (should the infant remain in the crib throughout an entire 24 hr period). Notably, infants are not always in their crib and it is not feasible to provide round-the-clock research staffing to monitor when the infant is in or out of the crib (e.g., being held

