by caregiver, fed, in motorized bedside glider – all part of the standard of care). The preprogrammed 3-hr duty cycle, 24/7, affords opportunity to capture periods when the infant is in the crib, and also conforms to routine timing of medication. Periods of stimulation will be complementary to standard of clinical care (e.g., clinically-determined pharmacological management; routine holding by caregiver or hospital-issued motorized glider; breast and/or bottle feed). A bedside log will indicate periods the infant is in the crib, being held, or placed in hospital-issued gliders/motorized seats. Infants will be scored for severity of withdrawal using standardized, modified Finnegan scoring system by clinical-care nurses per routine clinical care throughout hospitalization, and may receive pharmacological treatment as per standard care determined by the medical-care team at the respective institution.

2) SCC. No Intervention: Standard of Clinical Care (SCC). Newborn infants atrisk for NAS due to opioid exposure in utero randomized to this arm will be enrolled within 30-hours post birth and receive standard of care (e.g., clinically-determined pharmacological management; routine holding by caregiver or hospital-issued motorized glider; breast and/or bottle feed). Infants will be issued a hospital crib mattress. A bedside log will indicate periods the infant is in the crib, being held, or placed in hospital-issued gliders/motorized seats. Infants will be scored for severity of withdrawal using standardized, modified Finnegan scoring system by clinical care nurses per routine clinical care throughout hospitalization, and may receive pharmacological treatment as per standard care determined by the medical-care team at the respective institution.

2.1.3. Study Site. Studies will be conducted at the UMass Memorial Healthcare Neonatal Intensive Care Unit (NICU), Continuing Care Nursery (CCN), and Newborn Nursery (NN) – referred to as UMass - and at the Magee-Women's NICU and Well-Baby Nursery, and Mercy Hospital, of the University of Pittsburgh Medical Center – referred to as UPitt - where infants receive round-the-clock medical care. Studies for Aim 1 and Aim 2 will be performed at the infant's hospital bedside, outcome assessments for Aim 3 will be performed at respective hospital inpatient (if infant still hospitalized) and outpatient facilities.

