2) Chart Review/Bedside Log. NAS severity scores. The infant's clinical-care nurses at each site are routinely trained on the NAS assessment tool (modified

Finnegan Scale)^[63] as part of clinical education; this helps ensure reliability of scores. Nurses score the infants' withdrawal severity ~every 3-4 hrs to assess changes in central, autonomic, vasomotor and gastrointestinal function. Daily NAS scores, weight (gain/loss; trajectory), head circumference, routine feed type (formula or breast milk), pharmacological management (medication, dose normalized for body weight), and birth date and date of hospital will be obtained from medical and/or nursing chart review. A computerized and/or paper log (de-identified, subject id only) will be kept by the infant's bedside to record when the infant is in the crib, and nursing/parent interventions (e.g., feeds, diapering, caregiver cuddling, and placement in motorized swings). This provides some indication of the infant's routine clinical care since investigators cannot be at the bedside 24/7. A separate log kept by investigators will be used to record preprogrammed time onset and offset of SVS (i.e., to verify daily automated SVS coinciding with log indicating when infant is in the crib to receive the intervention). Data will be entered by a research investigator via secure password protected computer into REDCap database.

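### Section 4.3.2 offers feed type as a covariate and treatment interaction with no pre-randomisation time point, so the adjusted SVS effect is at risk of bias if feeding differs by arm

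*Combined protocol and SAP*

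**What the plan says.** Section 4.3.2 plans mixed effects models for NAS scores, morphine requirement, weight gain and length of stay. On covariates it says "Factors of interest will be included in the model as appropriate and interactions with treatment group will be tested as well", and it reads those tests as subgroup results: "The interactions will indicate whether the treatment effect is the same across subgroups". The selection criterion is goodness of fit: "A model will be fit for each outcome using Nagelkerke's R² to determine the model with the best fit". The list of factors covers drug exposure, demographic and birth variables, and finally "delivery mode, anesthesia at delivery), and feed type (formula or breast milk".

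Section 4.1.1, item 2 (Chart Review/Bedside Log) shows where feed type comes from. The chart items run "head circumference, routine feed type (formula or breast milk), pharmacological management", with no time point and no coding rule for infants whose feeding changes or is mixed.

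Section 2.1.2 describes care in both arms as including "routine holding by caregiver or hospital-issued motorized glider; breast and/or bottle feed". SVS is given "throughout hospitalization, starting within 30-hrs post birth". The SVS mattress vibrates and makes sound (2.1.1), while SCC infants have a hospital mattress (2.1.2). The design is labelled placebo-controlled, but no sham mattress and no blinding of caregivers is described.

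**The concern.** Drug exposure, sex, race, gestational age, birth measures, delivery mode and anesthesia are all settled by birth, so randomisation balances them in expectation and adjusting for them is safe. Feed type during the stay does not have that protection. It is largely determined after allocation, by people who can probably tell the arms apart.

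If allocation changes feed type, three things follow.

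- **Lost effect.** Any benefit of SVS that operates through feeding is subtracted from the adjusted effect.
- **Induced confounding.** If sicker infants are less likely to receive breast milk, then infants with the same feed type in the two arms no longer have the same average severity. The adjusted coefficient picks up that difference, in either direction.
- **A misleading subgroup.** A treatment-by-feed-type interaction would be read as a baseline subgroup finding, although membership was partly decided after treatment began.

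At stake are the adjusted Aim 1 effect promised in 2.4.1 and the feed-type interaction.

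**Working it through.** **The plan's own figure.** Section 2.4.1 gives 115 per group, SD 2.5, two-sided alpha 0.05 and 90% power for a difference of 1.1. The standard error of the difference is 2.5 × √(2/115) = 0.330. The detectable difference is (1.960 + 1.282) × 0.330 = 1.07, which rounds to 1.1; power at 1.1 is about 91%. The figure reproduces and is not in dispute. It serves here as the yardstick.

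**Timing of each listed factor.**

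| Factor in 4.3.2 | Fixed by birth? |
|---|---|
| Prenatal drug exposure | Yes |
| Gender, race, gestational age, birth weight, birth head circumference | Yes |
| Delivery mode, anesthesia at delivery | Yes |
| Feed type | No; time point undefined |

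**Does the selection rule screen feed type out?** No. Nagelkerke's R² rises with the likelihood, so adding a covariate to a nested model cannot lower it. The rule has no step that asks whether a covariate was measured before randomisation.

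**Size of the effect.** The documents give no feeding rates, so every input below except SD 2.5 and the 1.1-point effect is an assumption. The illustration uses one score per infant. With a shift *s* in the proportion on breast milk, a feed effect *b* on the score, and unmeasured severity U with effect *g*,

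adjusted − total = s × [ g × |cov(U, F)| / var(F) − b ],

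where F is feed type, cov and var are within arm, and severity lowers the chance of breast milk.

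*Scenario A: 40% breast milk in SCC, direct SVS effect −1.1, SD 2.5, s = 0.10.* Average var(F) = (0.40 × 0.60 + 0.50 × 0.50)/2 = 0.245.

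- No severity link: the change is 0.10 × (−b), which is 0.00, 0.10 or 0.20 for b = 0, −1 or −2.
- Weaker link (g = 1.25, average covariance 0.176): severity adds 0.10 × 1.25 × 0.176/0.245 = 0.09.
- Stronger link (g = 1.25, average covariance 0.278): severity adds 0.10 × 1.25 × 0.278/0.245 = 0.14.
- The largest case is 0.20 + 0.14 = 0.34 points.

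A simulation of 2,000,000 infants gave the same values. By size of shift:

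| Shift in breast-milk feeding | Adjusted effect smaller in size by |
|---|---|
| 0 points | 0.00 in every case |
| 5 points | 0.00 to 0.17 |
| 10 points | 0.00 to 0.34 |
| 20 points | 0.00 to 0.69 |

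*Scenario B: no SVS effect and no feed effect, 115 per group.* P(breast milk) = 0.40 + 0.15 × SVS − 0.15 × U, g = 1.2, residual SD 1.8. The expected bias is 0.15 × 1.2 × 0.15/0.245 = +0.11. Simulation gives 0.00 unadjusted and +0.11 adjusted. With the shift reversed to −15 points, the adjusted effect is about −0.12, a spurious benefit.

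*Would feed type be kept?* With a likelihood-ratio test at 0.05 standing in for fit-based selection, feed type was retained in about 72% to 76% of scenario B trials (4,000 replicates each), although it had no effect on the score. It was retained because it carries severity.

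**The case against.** The strongest reply is that the risk is conditional and confined to a secondary estimate. Nothing in the documents says SVS changes feed type, and with no shift the bias is zero. Factors enter only as appropriate. The covariates named in 4.3.1 omit feed type. Section 4.3.1 begins with unadjusted comparisons, and 2.4.1 powers Aim 1 on an unadjusted t-test and an overall treatment coefficient, with the adjusted effect as an addition. All of this stands, and it limits the reach of the point. It does not answer it, because the adjusted effect and the interactions are still planned.

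Four further points.

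- **Timing.** The chart list in 4.1.1 also contains birth date, so being in that list does not prove that feed type is a repeated measure. That is correct. What can be said is that no time point is defined, and feeding through the stay mostly follows enrolment within 30 hours of birth.
- **Milk type and feeding mode.** The covariate is milk type; 2.1.2 speaks of breast or bottle, which is mode. The 2.1.2 text shows that feeding is concurrent care, not that milk type responds to SVS.
- **Change of estimand.** Part of the movement, 0.20 of the 0.34 in the largest 10-point case, is effect through feeding that adjustment removes, not confounding. It is still a departure from the randomised comparison.
- **Scope of the list.** The factor list follows the latent-class sentence, but it uses the same term, factors of interest, as the sentence on model inclusion and interactions.

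A reader might also infer that parents keep SVS infants in the crib and therefore feed them differently. The documents do not support this: 2.1.2 says infants are not always in the crib, runs an automated cycle for that reason, and makes stimulation complementary to holding and feeding.

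**Conclusion.** The point holds as a risk of bias in the adjusted Aim 1 effect and in the feed-type interaction. A reader might infer that the adjusted effect is biased as planned. That goes too far: bias needs SVS, or knowledge of the arm, to shift feed type, and it needs feed type to affect the score or share causes with it. The documents give no figure for either. That caregivers can tell the arms apart is likewise an inference from the mattress descriptions, not a statement in the plan.

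If a 10-point shift occurred, the adjusted effect would move by 0.00 to 0.34 points, at most 0.34/1.1 = 31% of the design difference. With a 15-point shift and no feed effect, the movement is about 0.11 points, one third of the 0.33 standard error. Its sign depends on the direction of the shift, which cannot be known in advance. The unadjusted comparisons and the 115 per group are unaffected. The change is worth making because it is cheap and the risk is avoidable.

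**What to change.** In 4.3.2, exclude feed type during hospitalization from the covariates and from the treatment interactions of the treatment-effect models. If feeding is wanted as an adjuster or a subgroup, use only feed type or feeding intention recorded before randomisation, and say how infants without such a value are handled. With enrolment soon after delivery, some may have none. Report in-hospital feed type by arm, or use it only in a mediation analysis labelled exploratory. Section 4.3.4 refers to the same model-building strategies without repeating the factor list; apply the rule there too if feed type is carried over.

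The cost is SAP wording and a possible small loss of precision from dropping a prognostic covariate. How much of that a pre-randomisation value would recover cannot be calculated from the documents.

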1.1 Trial Objectives

This study investigates Stochastic Vibrotactile Stimulation (SVS) complementary to standard of care for treating NAS. Using a specially-constructed crib mattress we will determine if SVS reduces symptoms and duration of NAS and improves long term outcomes in intrauterine opioid-exposed newborns. Findings from this study will elucidate whether SVS has potential as a therapeutic treatment for drug-exposed newborns to reduce symptomatology, facilitate weaning and minimize hospitalization, with implications for better regulation of systems and improved developmental outcomes.

1.1.1. Specific Aims. The three areas to be investigated in this project are:

Specific Aim 1. Determine the efficacy of SVS as a non-pharmacological therapy complementary to standard clinical care (SCC) for reducing severity and duration of opioid withdrawal in newborns compared to SCC alone. Quantify clinical variables: NAS severity/administration of treatment, treatment days, days in hospital, velocity of weight gain, cumulative morphine dose, and longitudinal assessment of movement activity.

Specific Aim 2. Examine physiological responses to SVS compared to SCC at two stages of withdrawal severity. Measure cardio-respiratory stability, temperature regulation, and movement activity.

Specific Aim 3. Compare neurobehavioral outcomes in fetal drug-exposed infants between infants who received SVS and those who received SCC. Examine longitudinal outcomes assessments at 1 month, 6-months and 1 year to test whether early intervention with SVS compared to SCC improves physical, social, emotional and cognitive development.

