4.3.3. Specific Aim 2: Study design allows systematic quantification of condition effects on breathing (IBI variance and respiratory rate), cardiac rhythm (R-R variance and heart rate), movement activity (frequency and duration), blood oxygenation (durations<85%), and skin temperature. Histogram of frequency-bands of cardio, respiratory and movement incidents will be determined. As with Aim 1, mixed effects models will be used to examine if SVS, within infants and between SVS and SCC infants: 1) Decreases irritability and sleep disruption/fragmentation indexed by movement frequency and duration; 2) Improves cardio-respiratory control: reduces bradycardia/bradypnea. tachycardia/tachypnea and increases incidents of eucardia/eupnea; and 3) Reduces other NAS symptoms: e.g., temperature; oxygenation. Additional computational signal analysis. We have developed novel statistical point process algorithms that measure cardio-respiratory dynamics and movement over continuous time domains.^[67, 68]The variable characteristics of respiratory (IBI) and cardiac (RR) signals are integrated with the dynamic characteristics of these signals to provide instantaneous, moving estimate of mean, variance and other dynamic measures (e.g., spectrum, poles, frequency).^[68] These measures will be used to examine temporal dynamics of respiratory and heart rate rhythm, and explore corresponding physiological relationships with movement over time; e.g., Do IBI changes that reflect caudal brainstem function precede cortical behaviors such as arousal (e.g., movement)? Time series of movement periods will be analyzed using Wavelet derived SAP throughout stimulation ON and OFF to evaluate temporal dynamics including: 1) Response time for improvement in rhythm relative to the onset of stimulation; 2) Whether there is loss of efficacy over time (during each 30 min stimulus period as well as from one period to the next); 3) Whether improvement in rhythm persists following offset of stimulation.

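### Aim 2 is worded as SVS versus SCC but sized on a within-infant ON-OFF test, and the analysis examines both contrasts without saying which one answers the aim

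*Combined protocol and SAP*

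**What the plan says.** - **Aim (section 1.1.1).** "Examine physiological responses to SVS compared to SCC at two stages of withdrawal severity". The heading of 4.1.2 repeats this framing.
- **Analysis overview (4.3.1).** For all aims, the initial comparison is SVS versus SCC by two-sample t-test or a non-parametric equivalent. Treatment group is the fixed effect in the mixed models.
- **Sample size (2.4.2).** "We use Movement as primary outcome for this aim". The calculation proceeds "assuming a two-sided paired t-test at alpha=0.05 for the unadjusted treatment effect" and concludes: "we estimate 25 infants per group will give us 90% power to detect a reduction of 7% in movement between the two treatment groups". The same sentence restates that effect as "a relative reduction of about 20% from 40% in OFF to 33% in ON". The SD is described as "with a conservative SD of 10% (from the pilot study"), and the pilot SDs given are per condition (10% OFF, 9% ON).
- **Aim 2 analysis (4.3.3).** "mixed effects models will be used to examine if SVS, within infants and between SVS and SCC infants", with movement assessed by both frequency and duration, alongside cardio-respiratory, temperature and oxygenation outcomes.

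No section ranks the two contrasts, gives a multiplicity rule for Aim 2, or says what is concluded if only one contrast is significant.

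**The concern.** The two contrasts answer different questions. SCC infants lie on a hospital mattress (2.1.2), so ON-OFF can be estimated only among SVS infants and is not a comparison of randomised groups. SVS versus SCC is the randomised comparison, and it is the one the aim names.

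They can also disagree. If movement rebounds when stimulation stops, ON-OFF favours stimulation although SVS infants do no better than SCC infants. If benefit carries into the OFF period, SVS beats SCC while ON-OFF is null. Section 4.3.3 itself plans to look at whether improvement lasts after stimulation ends, so the second case is one the investigators consider possible.

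At stake is whether an ON-OFF result can be reported as the SVS-versus-SCC answer. Section 2.4.2 invites this, because it computes one contrast and describes the other.

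**Working it through.** **Inputs.** From 2.4.2: difference 7 points, SD 10, 25 per group, two-sided alpha 0.05. Assumed, because the documents do not give it: ON/OFF correlation r within an infant, 0.3 to 0.7.

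**1. The plan's own figure.** Paired t-test with 10 as the SD of the difference: noncentrality (7/10)·√25 = 3.5 on 24 df, power 91.9%; 24 infants are enough for 90%. The stated 90% is therefore reproduced as a paired test. If 10 is instead the SD of each condition, the SD of the difference is 10·√(2(1−r)):

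| r | SD of difference | Power, n = 25 |
|---|---|---|
| 0 | 14.1 | 66% |
| 0.3 | 11.8 | 81% |
| 0.5 | 10.0 | 92% |
| 0.7 | 7.7 | 99% |

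**2. The same inputs between arms.** Two-sample t-test on one condition: noncentrality 7/(10·√(2/25)) = 2.47 on 48 df, power 67.9% (69.7% by normal approximation). Power of 90% needs 44 per group (43 by normal approximation).

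**3. Error rate if either contrast at 0.05 counted and both nulls were true.** The correlation between the two estimates depends on how the between-arm contrast is formed:
- SVS session mean versus SCC: correlation 0, so 1 − 0.95² = 9.75%.
- SVS ON versus SCC: correlation √(1−r)/2 = 0.42 to 0.27, giving 9.3% to 9.6%.
- Difference in differences: correlation 0.71, giving 8.3%.

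Simulated t-tests with 25 per arm agree, at 0.082 to 0.098. Two tests at 0.05 cannot exceed 0.05 + 0.05 = 10%. Counting frequency and duration as well makes four tests: 1 − 0.95⁴ = 18.5% if independent. With an assumed frequency-duration correlation of 0.3 to 0.7, simulation gives 0.155 to 0.175, and a repeat that varied r and the between-arm definition gave 0.154 to 0.182.

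**4. How the contrasts can split.** Simulated with 25 per arm, SD 10 in each condition and r = 0.3 to 0.7. Entries are the percentage of trials significant at 0.05.

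| True means ON / OFF / SCC | ON-OFF | SVS ON vs SCC | SVS session mean vs SCC |
|---|---|---|---|
| Effect only while ON: 33 / 40 / 40 | 81-99 | 68 | 26-32 |
| Benefit persists: 33 / 33 / 40 | 5 | 68 | 75-85 |
| Rebound: 40 / 47 / 40 | 81-99 | 5 | 26-32 (almost all with SVS worse) |

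In the first row, exactly one of ON-OFF and SVS ON versus SCC is significant in 30-32% of trials. So even with the effect the plan assumes, about three trials in ten give a split result for which there is no rule.

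**5. Testing ON-OFF first.** If SVS versus SCC could be tested only after a significant ON-OFF result, its power in the second row would fall from 68% (ON) or 75-85% (session mean) to about 3-4%.

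**The case against.** The documents lean towards SVS versus SCC. The aim, the 4.1.2 heading and the analysis overview all say so, and 2.4.2 itself speaks of the two treatment groups. On that view the paired formula is a sample-size slip, and Aim 2 has an identifiable contrast. Aim 2 is also an acute physiology sub-study at one site, and Table 1 labels only Aim 1 outcomes as primary clinical outcomes, so strict family-wise control is partly a matter of preference.

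Much of this stands. It supports making the between-arm contrast decisive, and it limits how serious the point is. It does not remove the conflict: 4.3.3 still lists both contrasts unranked, and the only alpha and power stated for Aim 2 belong to the paired test.

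A reader might infer that the plan tests both contrasts at 0.05 and accepts either, so that the false-positive risk is 10% or more. The documents do not support that. For Aim 2, 0.05 is attached only to the paired test, no success rule is given, and two contrasts alone cannot exceed 10%. The higher range treats movement frequency as co-primary, although 2.4.2 sizes movement as percent of condition time.

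A reader might also think that a fixed sequence with ON-OFF first is a cheap remedy. Step 5 shows that it would nearly eliminate the randomised comparison when benefit persists.

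**Conclusion.** The point holds as a failure to specify the deciding contrast. Aim 2 is stated as SVS versus SCC, sized as ON-OFF and analysed as both, with no rule for a split result. The main consequence is interpretive: a non-randomised ON-OFF effect could stand as the between-arm conclusion.

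The error rate is secondary and conditional. It is about 8-10% for movement if a win on either contrast at 0.05 counts and both nulls are true, and about 15-18% only if frequency and duration both count, under an assumed correlation of 0.3 to 0.7. The power figures rest on the plan's 7 points, SD 10 and 25 per group. The split-result figures also rest on the assumed ON/OFF correlation. This should be corrected, but it does not affect Aims 1 or 3.

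**What to change.** In 2.4.2 and 4.3.3:

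1. Name percent of condition time moving, the quantity used in the sample size, as the single primary movement measure.
2. State that the Aim 2 SVS-versus-SCC conclusion rests on the randomised between-arm contrast. Define it as SVS ON or SVS session mean versus SCC, and say how the two withdrawal stages are combined. The choice matters: the session mean gains power if benefit persists and loses it if the effect is confined to ON.
3. Report within-infant ON-OFF as a separate result that supports only an acute effect in SVS infants. Do not make the between-arm test conditional on it.
4. Label movement frequency and the cardio-respiratory, temperature and oxygenation results exploratory.
5. Restate the 90% power as applying only to the paired ON-OFF contrast, say whether 10% is the SD of the paired difference, and give the between-arm power.

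These are wording changes and need no new data. The downside to state openly is that, with 25 per group, the decisive contrast has about 68% power for a 7-point difference (two-sample t-test, one condition). The sponsor must accept that or plan for about 44 per group.
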